The auto-PAP machines will record the number and type of respiratory events detected, the pressure delivered in response to these events and the amount of time that the machine was on and delivering pressure to a patient. All subjects will be instructed to use the device nightly during sleep, for the ensuing four months. Objective compliance checks will be conducted at 1 week, 1 month, and study completion, by having the subject present the PAP "Smartcard" for download and interpretation. To increase patient compliance and decrease variance in outcomes introduced from differing degrees of exposure to the intervention, we will employ standardized procedures for management of PAP currently employed at University of Miami PAP clinic. These include instructing subjects on machine and mask use and regular phone follow-up for troubleshooting as necessary. The study PI will review compliance downloads and instruct the Research Associates (RA) to contact participants if compliance is low or machine reported air leakage from mask is too high. This is will be done for both arms of the study. The RA will not be aware of the details of the compliance report or machine pressure delivered to maintain blinding. Daily compliance will be reported as the total number of hours of PAP use per 24 hour period. Patients who use PAP > 4 hours/night for more than 50% of the nights at 4 month follow-up will be classified as PAP compliant.

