### **Data Analysis:**

Feasibility: The SCI Service at Miami VA actively serves approximately 300 patients. The Miami Project maintains a database of persons who have volunteered their participation in research studies and a database of individuals who have participated in past studies and volunteered additional participation. The database currently contains 3400 persons whose ages and levels of injury match the sought study participants. The Detroit VA SCI service oversees the care of greater than 100 patients/year. The Rehabilitation Institute of Michigan provides care for 350 SCI individuals. We anticipate completion of enrollment by the second quarter of Year 4, with 100 patients enrolled for PSG from each site.

Sample size justification and power: We will recruit 200 participants who meet our eligibility criteria and anticipate an SDB prevalence of 0.50 in SCI participants. This will allow us to randomize 100 participants with SDB to PAP or placebo arm. The neurocognitive test best characterized in both SCI and SDB is the Paced Serial Addition Test (PASAT). The PASAT is our primary study outcome. A mean difference in PASAT scores of 7 discriminates between those with and without cognitive impairment in populations with and without SDB. Assuming a standard deviation of 9 and alpha of 0.05, a sample size of 40 per study arm has a power of 0.93 to detect a mean difference of 7 units. Assuming a PAP non-adherence rate and/or loss to follow-up of 40%, we will continue to have sufficient power (81%) to detect such a difference with our proposed sample size of 100. These findings would be in keeping with PASAT values obtained in non-disabled patients with SDB vs. controls, and PASAT performance in other populations (e.g. multiple sclerosis, mild traumatic brain injury).

Planned analyses: We will score questionnaires while blind to PSG data and group allocation using instructions provided by the questionnaire developer. We will first examine continuous variables for normality. For those variables without a normal distribution, we will explore appropriate transformations in an attempt to achieve normality. Continuous variables will be summarized as means and SD, and categorical variables will be summarized as frequencies. Prevalence of poor SQ will be calculated as the proportion of individuals who complete the PSQI with a score of  $\geq 5$ .

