#### Primary Hypothesis (Specific aim 1, Hypothesis 1b)

A test of the primary null hypothesis, that PAP intervention does not increase mean PASAT score against the 1-sided alternative hypothesis that PAP intervention increases mean PASAT, will be based on a general linear model (GLM). PASAT score is modeled as a function of PAP intervention, using an indicator variable with 1 indicating PAP and 0 the sham treatment. A 1 degree of freedom test based on an F statistic will be used to test for a positive coefficient for the PAP indicator. This modeling approach provides a unified framework that accommodates covariates including use of sedating medications, years of education, level of injury, duration of injury, pain severity, presence of anxiety or depression, compliance with PAP, and recruitment center, each of which may reasonably be anticipated to influence PASAT score. We plan to include these covariates in our primary hypothesis test, which will be carried out at  $\alpha = 0.05$ . If the null hypothesis of no effect is rejected, computation of 95% confidence limits on the estimate of treatment difference in PASAT score mean will be carried out.

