#### Control of False Positive Rate of Inference

The inference of primary interest in this study is the effect of treatment on PASAT score. Because the test for intervention on PASAT is considered pre-planned, it will be carried out at  $\alpha$ -level 0.05. Similarly, tests for effects on groups of CV biomarkers, sleep, mood and quality-of-life measurements

are considered pre-planned in the sense that measurements in each group will be subjected to statistical testing regardless of test outcome for PASAT. Accordingly, tests for multiple measurements taken in each category of biomarkers will be carried out at  $\alpha$ -levels below 0.05. This approach recognizes that multiple testing is involved within each biomarker category and adjusts the significance level for individual tests downward to control the false positive inference rate at the category level. We will apply a False Discovery Rate (FDR) criterion of 5% separately for each category, thereby acknowledging the substantial overall number of tests per category but preserving power to detect true effects for each type of biomarker.

Primary analyses will be conducted in accordance with the intention-to-treat principle. We will also repeat analyses using a per protocol viewpoint. We will use statistical software, SPSS for Windows version 19 for all analyses.

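### The 81% power after 40% non-adherence and/or loss does not follow from its stated inputs (91% one-sided, 84% two-sided), and it pools loss with non-adherence under an intention-to-treat analysis

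*Combined protocol and SAP*

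**What the plan says.** All of the power material is in the sample size and power paragraph under Data Analysis. It names the endpoint ("The PASAT is our primary study outcome"), takes a difference of 7 points, an SD of 9 and alpha 0.05, and states that "a sample size of 40 per study arm has a power of 0.93 to detect a mean difference of 7 units". It then continues: "Assuming a PAP non-adherence rate and/or loss to follow-up of 40%, we will continue to have sufficient power (81" per cent) "to detect such a difference with our proposed sample size of 100". It does not say whether alpha is one- or two-sided, how the 40% divides between loss and non-adherence, or how a non-adherent participant enters the calculation.

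Three other places bear on the figure:

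- The Primary Hypothesis section tests the null "against the 1-sided alternative hypothesis that PAP intervention increases mean PASAT", at 0.05, in a linear model. Its covariates include "compliance with PAP, and recruitment center, each of which may reasonably be anticipated to influence PASAT score".
- The section on control of the false positive rate states: "Primary analyses will be conducted in accordance with the intention-to-treat principle". A per-protocol repeat is also planned.
- The Intervention section defines adherence: use above 4 hours a night "for more than 50% of the nights at 4 month follow-up will be classified as PAP compliant".

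**The concern.** There are two problems in one sentence.

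The first is arithmetic. Removing 40% of 100 leaves 30 per arm, and power there is not 81% on either sidedness.

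The second is the pooling. Saying that power is kept for the same difference suggests that the full 7 points was retained and that non-adherers were treated as if they had left the trial, although the calculation is not shown. The primary analysis does not treat them that way. A participant who stops using PAP but returns for the four-month PASAT is analysed in the PAP arm. The sample is then not reduced, but the expected difference may be.

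This sentence is the plan's only evidence that power survives 40% non-adherence and/or loss. If it cannot be reproduced, and could be off in either direction, it does not support the claim that power is sufficient.

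**Working it through.** **Inputs from the documents.** Difference 7, SD 9, alpha 0.05, 100 randomised and 40% non-adherence and/or loss (sample size and power paragraph); 1:1 allocation, so 50 per arm (Randomization Protocol); one-sided primary test (Primary Hypothesis section).

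**Method.** Two-sample t-test. The standard error is SE = SD × √(1/n₁ + 1/n₂), the noncentrality is λ = difference / SE, and df = n₁ + n₂ − 2. One-sided power is the probability that a noncentral t(df, λ) exceeds the 95th percentile of central t. The two-sided version uses the 97.5th percentile and adds the negligible lower tail.

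**Step 1: reproduce the companion figure.** With 40 per arm, SE = 9 × √(2/40) = 2.012, λ = 7/2.012 = 3.478 and df = 78. The critical values are 1.665 and 1.991. Power is 0.964 one-sided and 0.930 two-sided, so the stated 0.93 is a two-sided figure.

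**Step 2: the 81%, read as removal.** With 50 × 0.6 = 30 per arm, SE = 9 × √(2/30) = 2.324, λ = 7/2.324 = 3.012 and df = 58. The critical values are 1.672 and 2.002. Power is **0.909 one-sided and 0.842 two-sided**.

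Other removal readings at difference 7 and SD 9:

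| Reading | n per arm | One-sided | Two-sided |
|---|---|---|---|
| 40% off both arms of 50 | 30, 30 | 0.909 | 0.842 |
| 40% off the 40-per-arm case | 24, 24 | 0.844 | 0.751 |
| 40% off the PAP arm only | 30, 50 | 0.955 | 0.914 |

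None gives 0.81. Working backwards, about 81% needs 22 per arm one-sided (0.814) or 27 to 28 per arm two-sided (0.801, 0.815). Those correspond to losing 56%, or 44–46%, of each arm, not 40%. Taking 8 to 12 degrees of freedom for covariates at 30 per arm changes little: 0.907–0.908 one-sided and 0.839–0.840 two-sided.

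**Step 3: separate loss from retained non-adherence.** The following are assumptions, not in the documents: 7 points is the effect in users; non-users get zero benefit (a lower bound) or half; loss is equal and non-informative in both arms; the sham arm is unaffected by adherence; there are no covariates.

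If a fraction q of the analysed PAP arm is non-adherent and keeps a fraction k of the benefit, the expected difference is 7 × [1 − q(1 − k)].

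- 20% lost, 20% non-adherent, no benefit: n = 40, q = 0.20/0.80 = 0.25, difference = 7 × 0.75 = 5.25.
- No loss, 40% non-adherent, no benefit: n = 50, difference = 7 × 0.60 = 4.2.
- No loss, 40% non-adherent, half the benefit: n = 50, difference = 7 × 0.80 = 5.6.

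Mixing users and non-users also widens the PAP arm: its variance is 81 + [7(1 − k)]² × q(1 − q). This gives √(81 + 49 × 0.1875) = 9.50, √(81 + 49 × 0.24) = 9.63 and √(81 + 12.25 × 0.24) = 9.16. The sham SD stays at 9.

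| Case | SD fixed at 9: one-sided / two-sided | With mixture variance: one-sided / two-sided |
|---|---|---|
| 40% lost | 0.909 / 0.842 | not applicable |
| 20% lost, 20% non-adherent, no benefit | 0.827 / 0.731 | 0.808 / 0.708 |
| 40% non-adherent, no benefit | 0.749 / 0.637 | 0.723 / 0.607 |
| 40% non-adherent, half the benefit | 0.926 / 0.869 | 0.922 / 0.863 |

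A simulation with random adherence status (200,000 runs per case) agreed with the mixture-variance column to within 0.002.

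**The case against.** The strongest reply is that the error is small and on the safe side. The neighbouring 0.93 is two-sided, so the like-for-like comparison is 84% against 81%, a gap of 3 points. Read as loss, the plan understates its power. That is right for loss, but it does not extend to non-adherence, where power can fall below 81%.

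A second reply is that 81% may come from an undisclosed calculation. Some routes come close: the 20%/20% split (81–83% one-sided), a two-sided rank test with efficiency 3/π (82.4%), or an SD of 9.4 in place of 9 (81.0% two-sided). Each needs an input that the plan does not state. The first also mixes a one-sided figure with a two-sided 0.93, the second is not the planned linear model, and the third contradicts the stated SD.

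A third reply is that 7 may be the target between-arm difference, not the effect in users. Retained non-adherers would then make a 7-point difference less likely to arise without lowering the power to detect it. This is a fair reading. It is the reason the dilution figures are labelled as conditional on an assumption. On that reading, however, non-adherence has no place in the power sentence, and only loss should reduce the sample, giving 91% (84%) if all 40% is loss.

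Finally, the planned per-protocol repeat could be the intended setting. Removing non-adherers gives 91% (84%) from both arms, or 95% (91%) from the PAP arm alone, so it does not recover 81% either.

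**Conclusion.** The concern holds. The stated 81% is wrong as written in the sense that no removal reading of its own inputs returns it. The plain reading gives 91% on the planned one-sided test, and the two-sided method behind the adjacent 0.93 gives 84%. This part rests only on figures in the plan and is firm.

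The pooling is the more consequential defect. Depending on what the 40% consists of, one-sided power for the simple intention-to-treat contrast runs from 72–75% to 92–93% (two-sided, 61–64% to 86–87%) across the cases examined. Those bounds depend on the assumptions listed with the calculation, above all on 7 points being the effect in users and on how much benefit non-adherers keep. Zero benefit is deliberately a lower bound, because the plan's compliance cut-off classes some people with real use as non-compliant.

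Nothing here shows the trial to be too small. The power statement should be corrected, but it is not a reason to change the design.

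**What to change.** Rewrite the power paragraph under Data Analysis to do the following:

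- State the sidedness of alpha and put both power figures on the same test. On the planned one-sided test, 0.93 at 40 per arm becomes 0.96.
- Replace the 81% with one-sided (two-sided) power that separates the mechanisms: 40% lost, 91% (84%); 20% lost plus 20% non-adherent with no benefit, 81–83% (71–73%); 40% retained non-adherers with no benefit, 72–75% (61–64%), or with half the benefit, 92–93% (86–87%). The sponsor's own expected rates, if available, should replace the illustrative split.
- Declare the assumptions: 7 points in users, the benefit assumed in non-users, the SD convention (fixed at 9, or 9 within users and within non-users), equal non-informative loss, and no covariates.
- Note that these figures describe the simple intention-to-treat contrast. With PAP compliance as a covariate, as the Primary Hypothesis section plans, the PAP coefficient is not that contrast.
- If 81% came from another calculation, show it.

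The cost is one paragraph of wording. The pure-loss figure becomes more favourable than 81%, and the figure for retained non-adherers with no benefit becomes less favourable. Sample size, endpoint and analysis stay as they are.

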### ***Sleep Questionnaires***

1) Sleep Quality (SQ): We will assess sleep quality using the Pittsburgh Sleep Quality Index (PSQI). The PSQI is the most widely used global sleep assessment tool. Validity and test-retest reliability of this instrument has been extensively studied. A global PSQI score greater than 5 yields a diagnostic sensitivity of 89.6% and specificity of 86.5% (kappa = 0.75, p < 0.001) in distinguishing 'good' and 'poor' sleepers.

[figure not shown]
2) Chronic Insomnia: We will use the Athens Insomnia Scale (AIS) to assess insomnia in the study population. It consists of eight items: the first five pertain to sleep induction, awakenings during the night, final awakening, total sleep duration, and sleep quality; while the last three items refer to well-being, functioning capacity, and sleepiness during the day. Reliability and validity for the instrument have been well documented.

3) Screening for SDB: We will screen for increased risk of SDB using the Berlin questionnaire (BQ). This is a validated questionnaire with good performance characteristics in the general population. It has been successfully used by our group in the SCI population (see preliminary data).

4) Daytime Sleepiness: Epworth Sleepiness Score (ESS) is a valid measure of subjective daytime sleepiness. Eight items are rated on a scale of 0–3, total scores range 0–24, with higher scores indicating a greater propensity to fall asleep in different situations. In samples of sleep apnea patients, it shows high internal consistency and correlates well with objective measures of sleep latency. It has successfully been used in SCI individuals.

5) Impact of Sleepiness on Functioning: The Functional Outcomes of Sleep Questionnaire (FOSQ) is the gold-standard, disease specific instrument designed to assess the impact of sleepiness on the ability to conduct daily activities. The FOSQ has proven validity and reliability, and is sensitive to treatment changes. There are 30 items, which are divided into 5 scales: Activity, Vigilance, General Productivity, Social Outcome, and Intimacy and Sexual Relationships. These scales are summed to make a total score. Higher scores on the FOSQ indicate self-perceived better daily functioning. The FOSQ has been used by our team in a previous study of acute SCI and sleep disorders.

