#### Secondary Hypotheses

A second phase of analysis will focus on CV biomarkers and measures of sleep quality, quality of life, mood and pain. These analyses are considered exploratory in nature and hence will benefit from comparisons within as well as between groups.

For within group contrasts, initial observations serve as baseline for assessing the effect of treatment at 4 months. As in a classical paired design, inference focuses on the difference between baseline and 4 month observations. Hence, individuals serve as their own control for an effect of intervention. The null hypothesis that the baseline does not differ from the 4 month measurement is tested using statistical methods for a paired design. For normally distributed measurements, a paired t test will be used. For variables that depart from normality and cannot be transformed to approximate normality, a Wilcoxon signed rank test will be used.

Comparisons between PAP and sham treatment groups at 4 months will be made based on the linear model described above for the primary endpoint. In contrast to PASAT, however, tests for treatment group differences of CV biomarkers and measures of sleep quality, HRQOL, mood and pain will be 2-sided. Because the number of secondary hypotheses to be tested is potentially large, these tests will be considered exploratory in nature. Accordingly, control of the false positive inference rate for these tests will be carried out at the group level, as described below, rather than for the entire set of secondary analyses. Similar approach will be taken for the analyses of select measures at the one month time-point.

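### Poor sleep quality is counted at PSQI ≥5, but the only cut-off the protocol supports is a score above 5, so the reported prevalence can only be equal or higher

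*Combined protocol and SAP*

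**What the plan says.** The combined protocol and SAP mentions a PSQI cut-off in two places.

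- **Sleep Questionnaires, item 1 (Sleep Quality).** The instrument is supported by its published accuracy in separating good from poor sleepers: "A global PSQI score greater than 5 yields a diagnostic sensitivity of 89.6% and specificity of 86.5" per cent, with "kappa = 0.75, p < 0.001".
- **Data Analysis, planned analyses.** The reporting rule is "Prevalence of poor SQ will be calculated as the proportion of individuals who complete the PSQI with a score of" ≥5. The quoted words stop just before the symbol, which the document prints as greater than or equal to.

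The planned-analyses paragraph also says that questionnaires are scored "using instructions provided by the questionnaire developer". It gives no reason for a poor-sleep threshold different from the one cited earlier, and no other section mentions a PSQI cut-off.

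The largest possible denominator comes from the sample size paragraph: "We will recruit 200 participants who meet our eligibility criteria". The analyses of sleep quality by treatment are described under Secondary Hypotheses: "These analyses are considered exploratory in nature and hence will benefit from comparisons within as well as between groups".

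**The concern.** A score above 5 and a score of 5 or more are different decision rules. The protocol cites sensitivity and specificity for the first and plans to report prevalence with the second. Someone scoring exactly 5 is not a poor sleeper under the cited cut-off but is counted as one under the reporting rule.

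Two things follow. The quoted accuracy says nothing direct about the classification that will be reported. And two analysts, one working from the questionnaire section and one from the analysis section, would report different prevalences from the same data. Describing sleep quality in people with SCI is among the benefits claimed under Study Relevance and Applicability of Proposed Findings, so the figure is likely to be reported and should rest on one rule.

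**Working it through.** **Inputs from the document**

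- Cited cut-off: >5, with sensitivity 0.896, specificity 0.865 and kappa 0.75 (Sleep Questionnaires).
- Reporting rule: ≥5 (Data Analysis, planned analyses).
- Denominator: at most 200 (sample size paragraph). The rule counts only those who complete the PSQI, so it may be fewer.

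**Inputs assumed, because the document does not give them**

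- The global score takes whole numbers from 0 to 21.
- The score is roughly normal, with mean between 6 and 10 and SD between 3 and 4.

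**Step 1. Do the cited figures fit together?** Let p be the share of true poor sleepers, also not given. Then

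- observed agreement: Po = 0.896p + 0.865(1 − p)
- share testing positive: t = 0.896p + 0.135(1 − p)
- chance agreement: Pe = pt + (1 − p)(1 − t)
- kappa = (Po − Pe)/(1 − Pe)

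At p = 0.50: Po = 0.8805, t = 0.5155, Pe = 0.5000, so kappa = 0.3805/0.5000 = 0.761. The same formula gives 0.749 at p = 0.40 and 0.751 at p = 0.65. The stated 0.75 is therefore compatible with the stated sensitivity and specificity, and nothing suggests that the cited figures are garbled.

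**Step 2. Where do the rules differ?** Of the scores 0 to 21, those with score ≥5 but not >5 are {5}. So

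prevalence(≥5) − prevalence(>5) = P(score = 5) ≥ 0.

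The direction is certain: the ≥5 rule cannot give a lower prevalence. Against the same reference standard, its sensitivity cannot be lower than that of >5, and its specificity cannot be higher. The document gives no accuracy figure for ≥5.

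**Step 3. How large could the difference be?** With mean m and SD s, discretised and rescaled to 0–21:

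P(5) = [Φ((5.5 − m)/s) − Φ((4.5 − m)/s)] / [Φ((21.5 − m)/s) − Φ((−0.5 − m)/s)]

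For m = 8, s = 4: numerator Φ(−0.625) − Φ(−0.875) = 0.0752; denominator Φ(3.375) − Φ(−2.125) = 0.983; P(5) = 0.0765. Prevalence is then 74.6% at >5 and 82.3% at ≥5.

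| Mean | SD | P(score = 5) | Of 200 |
|---|---|---|---|
| 6 | 3 | 12.7% | 25.4 |
| 7 | 3.5 | 9.8% | 19.6 |
| 8 | 4 | 7.7% | 15.3 |
| 9 | 4 | 6.1% | 12.2 |
| 10 | 4 | 4.6% | 9.2 |
| 10 | 3.5 | 4.1% | 8.3 |
| 10 | 3 | 3.3% | 6.7 |

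Over means of 6, 7, 8, 9 and 10 combined with SDs of 3, 3.5 and 4, the extremes are the first and last rows: about 3–13%, or 7–25 of 200.

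**Step 4. What else uses the threshold?**

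- Primary test: PASAT score in a linear model, with no PSQI term among the listed covariates.
- Sample size: built on a PASAT difference of 7 and SD of 9.
- Eligibility and randomisation: randomisation requires AHI ≥10, and the listed criteria contain no PSQI condition.
- Hypothesis 1a model: insomnia is a covariate, but insomnia is assessed with the Athens Insomnia Scale.
- Sleep-quality comparisons: paired baseline-to-4-month differences and the same linear model between arms, neither stated to use a good/poor split.

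Only the descriptive prevalence depends on the rule.

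**The case against.** The strongest reply is that this hardly matters. The threshold appears once, for a descriptive proportion. No aim or hypothesis divides participants into good and poor sleepers, and no treatment-effect estimate, error rate or power figure changes. That stands, and it is why the severity is low.

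A second reply is that the questionnaire section only reports a published cut-off and does not adopt it as the trial's definition, whereas the protocol does say outright that it defines SDB as AHI ≥10. On that view the only operational rule is ≥5, and there is nothing to contradict. The first half is fair. It means that a reader should not infer that participants scoring 5 are misclassified in any absolute sense: the document does not show their true sleep status, and the statement holds only relative to the cited cut-off. But the reply leaves the reporting rule without any support in the document, beside accuracy figures that belong to a different rule.

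A reader might also infer that the resulting prevalence could never be compared with studies that use >5. The document does not support that. The global scores are collected, so prevalence at >5 can be recalculated from the same data without loss, and normally distributed or not, continuous variables are to be summarised by mean and SD in any case.

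Finally, the reference to developer instructions might be thought to settle the matter. Those instructions are not reproduced, so on the document alone they cannot decide between the two rules.

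**Conclusion.** The inconsistency is real: accuracy is cited for one rule, prevalence is planned with another, and nothing reconciles them. That conclusion and the direction of the difference need no distributional assumption. The size does. The 3–13% range rests on an assumed near-normal PSQI with mean 6–10 and SD 3–4, and the counts of 7–25 take the full 200 as completing the questionnaire. A different distribution would give a different figure. This is a low-severity consistency correction to a descriptive result, and it has no bearing on the trial's primary conclusion.

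**What to change.** In the planned analyses, change the rule for poor sleep quality from a PSQI score of ≥5 to a PSQI global score >5, so that it matches the Sleep Questionnaires section and the cited sensitivity and specificity apply to the rule used.

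The cost is one symbol, with no new data and no change to trial conduct. The stated prevalence will be slightly lower, by whatever share of participants score exactly 5.
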